8.1. Overall Summary of Tolerability

Overall summary table, including number of patients with:

- TEAEs
- Serious AEs (TESAEs)
- Study drug related TEAEs
- TEAEs by severity
- TEAEs leading to dose reduction
- TEAEs leading to treatment discontinuation
- TEAEs leading to death

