7.2.1. Management of Patients after Permanent Discontinuation of Study Drug

If study drug is permanently discontinued, the patient should be encouraged to remain in the trial to continue to obtain outcome measures and safety data via a phone or video call.

There are several options for a patient after permanently discontinuing study drug:

- Patient agrees to continue to return to clinic for all remaining in-clinic study visits and agrees to all planned remote visits.

- Patient only agrees to complete the early discontinuation (ED) visit as soon as possible after the decision is made, the follow-up visit 4 weeks after the last dose taken, and additional follow-up visits dependent upon lab results; it is preferred these are done in clinic but can be done remotely if that is not feasible.
- Patient only agrees to complete the ED visit; it is preferred this is done in clinic but can be done remotely if that is not feasible.
- Patient only agrees to remote visits to obtain patient study data.
- Patient agrees to a mix of remote and in-clinic visits to obtain study data
- Patient only agrees to allowing contact for determination of vital status
- Patient withdraws consent (see [Section 7.6](#)) and does not agree to any further study procedures or visits.

Assessments obtained at the early discontinuation (same as FU Visit at Week 52) are listed in the Schedule of Activities. Details of the assessments to be performed at the additional visits following drug discontinuation, should the patient agree to be followed via either in-clinic or remote visits, can be found in the Study Manual.

Patients that have not withdrawn consent and have difficulty returning for all remaining study visits can be contacted by phone or video call to obtain patient study data.

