7.6. Patient Consent Withdrawal

Patients have the right to withdraw consent and no longer participate in the trial at any time and for any reason without prejudice to their future medical care by the physician or at the institution. Consent withdrawal means the patient no longer wishes to undergo any follow-up visits, study procedures, investigator contact, and non-patient contact follow-up (eg, medical records check).

- Discontinuing study drug should be distinguished from consent withdrawal for follow-up since the patient may agree to undergo study procedures or still be contacted even though they have stopped taking study drug.

- Consent withdrawal should be accompanied by documentation of the reason for withdrawal for patients willing to provide it. If the patient is unwilling to provide the reason, that should be recorded.

Patients who withdraw consent should be asked explicitly about the contribution of possible AEs to their decision to withdraw consent, and any AE information elicited should be documented.

Preferably, the patient should withdraw consent in writing and, if the patient or the patient's representative refuses or is physically unable, the site should document and sign the reason for the patient's failure to withdraw consent in writing; if the patient is unwilling to provide the reason, that too should be documented. The ICF for the trial should note that although a patient is free to leave the trial and stop taking study drug, the investigators hope the patient will remain for follow-up status evaluations.

For patients who have withdrawn consent for further follow-up, investigators may review public records as permitted by applicable law to determine vital status of the patient at the end of the trial or before.

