8.3.1.4. Severity of Adverse Events

The investigator must assess the severity for each AE and SAE reported during the trial.

Severity describes the intensity (severity) of a specific event and is different from seriousness, which is based on patient/event outcome or action criteria and serves as a guide to determine the regulatory reporting obligations. The severity should be assessed by assigning a Grade of 1, 2, 3, 4 or 5 according to the Common Terminology Criteria for Adverse Events (CTCAE), version 5.0, as defined below:

- Grade 1 (Mild): asymptomatic or mild symptoms; clinical or diagnostic observations only; intervention not indicated.
- Grade 2 (Moderate): minimal, local or noninvasive intervention indicated; limiting age-appropriate instrumental activities of daily living (ADL)*.
- Grade 3 (Severe): Severe or medically significant but not immediately life-threatening; hospitalization or prolongation of hospitalization indicated; disabling; limiting self-care ADL**.
- Grade 4 (Life-Threatening): Life-threatening consequences; urgent intervention is indicated
- Grade 5 (Fatal): Death related to AE

* Instrumental ADL refers to preparing meals, shopping for groceries or clothes, using the telephone, managing money, etc.

**Self-care ADL refers to bathing, dressing and undressing, feeding self, using the toilet, taking medications, and not bedridden.

If the severity of an AE worsens during IP administration, only the worst severity should be reported on the AE page. If the AE lessens in intensity, no change in the severity is required.

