9.2.4.2. Serious Adverse Events

All SAEs will be summarized by system organ class, preferred term, the early-start and delayed-start treatment groups and overall, and by riluzole and edaravone use at baseline. Listings will be presented for patients who died and/or experienced serious AEs.

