8.2. Adverse Events

8.2.1. Summaries of Adverse Event Incidence Rates for All Subjects

Adverse events (AEs) will be coded by System Organ Class (SOC) and Preferred Term (PT) using the Medical Dictionary for Regulatory Activities (MedDRA) version 26.0.

Analyses of AEs will be performed for those events that are considered treatment emergent AEs (TEAEs), where treatment emergence is defined as any adverse events with an onset after initiation of study drug dosing in CY 5032, or an AE present at initiation of study drug dosing that worsens in severity after initiation of study drug dosing. If an AE had the onset in the preceding study CY 5031 and carry over to the open-label extension, it will not be considered as treatment emergent in CY 5032 data.

The following summaries of AEs and serious AEs (SAEs) will be presented by overall:

- TEAEs by SOC and PT
- TEAEs by PT
- TEAEs by SOC, PT and Severity (Grade 1-5)
- TEAEs related to study drug by SOC and PT

- TEAEs related to study drug by PT
- TESAEs by SOC and PT
- TESAEs by PT
- TESAEs related to study drug by PT
- TEAEs leading to drug discontinuation by PT
- TEAEs leading to death

AE summaries will be presented by descending order of PT in the overall column, and if applicable, SOC will be ordered first, with PT sorted within the SOC.

A patient will be counted only once within each SOC and PT. For the summary of AEs by severity, patients will be counted only once within each primary SOC/preferred term and will only be counted under the maximum severity.

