9. CHANGES TO PROTOCOL-SPECIFIED ANALYSES

As the study is prematurely stopped by Sponsor's decision, no formal statistical analysis will be produced. Only disposition, demographic and baseline characteristics, an overview of AEs and abnormal liver lab results will be summarized by table. By-subjects data listing will be produced for those with liver abnormality.

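### The SAP names death only as a TEAE outcome and does not say what becomes of the protocol's listing of patients who died, so some known deaths can go uncounted

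*SAP*

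**What the plan says.** SAP 8.1 counts patients with "TEAEs leading to death", and SAP 8.2.1 repeats the same item among the AE tables. The severity table in 8.2.1 runs up to Grade 5, which protocol 8.3.1.4 defines as "Grade 5 (Fatal): Death related to AE". Serious events are tabulated too. Both of these outputs are again limited to treatment-emergent events.

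SAP 8.2.1 defines a TEAE as "any adverse events with an onset after initiation of study drug dosing in CY 5032", or as an AE already present at first dose that then becomes more severe. The next sentence rules out any AE that began in CY 5031 and continued into the extension. No end to the TEAE window is given.

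The protocol is broader on deaths. Section 9.2.4.2 says: "Listings will be presented for patients who died and/or experienced serious AEs". It also follows survival beyond treatment. The options after permanent discontinuation in 7.2.1 include "Patient only agrees to allowing contact for determination of vital status", and for patients who have withdrawn consent, 7.6 says that "investigators may review public records as permitted by applicable law to determine vital status of the patient".

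SAP Section 9, which declares the departures from the protocol, restricts the tables to a short list that does not mention deaths. On listings it says: "By-subjects data listing will be produced for those with liver abnormality". SAP Section 7 keeps only a descriptive ALSFRS-R summary, so no survival analysis remains.

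**The concern.** Long-term safety is the primary objective (SAP 2.1.1), and protocol 8.3.1.7 describes ALS as uniformly fatal. Any reader of the abbreviated report will want to know how many treated patients died. A count filtered through the TEAE definition answers a narrower question: how many died of an AE that was recorded and classed as treatment emergent. With the survival endpoints gone, no other planned output gives deaths from any cause.

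The omission would not fall at random. The deaths at risk of being left out are those of patients whose fatal event was already under way at rollover, or who stopped or withdrew and were followed only for vital status.

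**Working it through.** The plan gives no death rate or expected number of deaths, so there is no figure to reproduce and no arithmetic to run. The check is to take each kind of death through the collection rules and then the output rules.

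1. **Fatal SAE with onset after the first CY 5032 dose, on or off drug.** Death makes an event serious (protocol 8.3.1.2). ALS signs that are otherwise exempt from AE recording must be recorded once they meet an SAE criterion (8.3.1.7). SAEs are recorded through end of study or four weeks after last dose, whichever is later (8.3.1.8), and end of study is the last patient's last visit (4.2). The SAP's TEAE definition has no end date. Result: counted. It would be lost off drug only if the last-dose cut-off for safety summaries in protocol 9.2.4 were applied, and the SAP does not say that it is.

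2. **Fatal AE with onset in CY 5031.** An AE below Grade 5 at rollover that becomes fatal has worsened in severity, because Grade 5 is the top of the scale. The worsening clause in SAP 8.2.1 therefore admits it. The carry-over sentence that follows excludes it, with no exception for a fatal outcome. Protocol 9.2.4.1 has the worsening clause but no such exclusion. Result: excluded if the carry-over sentence is followed, and the two sentences conflict.

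3. **Death known only from vital-status contact or public records.** Protocol 7.2.1 and 7.6 allow this information to be obtained. The SAE duty in 8.3.1.8 covers events that the investigator observes or the patient reports, and a public-record finding is not clearly either. If no SAE is entered, no AE table can show the death.

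4. **Late death judged unrelated to study drug.** For a patient who stopped early, the period from the end of the 4-week follow-up to end of study falls under two rules. Protocol 8.3.1.8 would have the SAE recorded. Protocol 8.3.1.9 asks for new SAEs after that follow-up only if they are judged drug-related. Result: capture is uncertain.

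The other outputs were then checked for cases 2 to 4:

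- The Grade 5 and serious-event tables in SAP 8.2.1 carry the same TEAE filter, so they add nothing.
- The disposition table (SAP 6.1) gives reasons for stopping drug and/or study, and death is one of the reasons in protocol 7.2. So are patient request, ALS progression, loss to follow-up and a sponsor request. A patient who withdrew consent and later died would most likely stand under the withdrawal.
- SAP 5.3 promises listings that support the tables without naming them. A listing that supports a table of fatal TEAEs inherits that table's restriction.

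**The case against.** The strongest reply is that most deaths are already covered. A reader might infer that the fatal-TEAE row is the only place where a death can appear, or that any death after stopping drug is lost. The documents support neither. The row is the only kind of output that names death, but disposition reasons can show deaths as well, and an off-drug fatal SAE with onset after first dose is recordable and meets the open-ended TEAE definition.

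A reader might also infer that the protocol's listing has been cancelled. That is not shown. In SAP Section 9 the word of restriction governs the tables, the liver-listing sentence is not worded as exclusive, SAP 5.3 allows unnamed listings, and the display shells are in separate documents (SAP 11.1, 11.2) that are not available here. What can be said is that the SAP neither names the listing nor declares it dropped.

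The carry-over case can be questioned too. Dyspnoea is among the ALS signs exempt from routine AE recording in this protocol (Table 4). CY 5031's own recording rules are not in the documents, so there may be no earlier AE to carry over and the later fatal event would be a new SAE. That reduces how often the case arises. It does not remove the conflict between the two sentences where an earlier AE does exist.

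Finally, cases 3 and 4 are partly collection questions in the protocol, and an all-cause row to last known vital status goes beyond the safety window in protocol 9.2.4, in a study whose analysis was deliberately cut back after futility. This is fair. The row is an improvement to the plan, not the repair of an error in it. But the abbreviated scope does not explain the silence about a listing that the protocol promised.

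**Conclusion.** The point holds in a limited form. The SAP has no count of deaths from any cause, its outputs that name death are restricted to TEAEs, and the fate of the protocol's listing of patients who died is not stated. Two kinds of known death can fall outside the death count as written (carried-over fatal AEs, and deaths known only as vital status). A third may do so (late unrelated deaths).

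The size cannot be estimated. The documents give no death rate, no share of patients followed for vital status only, and no count of AEs ongoing at rollover. A reader might be tempted to apply assumed percentages to the roughly 400 patients anticipated in SAP 3.2. That would not be sound, because the study was stopped early and both enrolment and follow-up may be well short of plan.

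The conclusion assumes that the carry-over sentence is applied as written, that a vital-status death is not always also entered as an SAE, and that the unseen shells do not already contain an all-cause death listing. If they do, the remaining task is to name it in the SAP and to settle the TEAE definition.

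**What to change.** - **SAP 8.1:** add one count of deaths from any cause in the Safety Analysis Set, from first CY 5032 dose to last known vital status, regardless of TEAE status and drawn from AE, disposition and vital-status data. Split it at 28 days after last dose, which matches the four-week SAE period in protocol 8.3.1.8 (4 x 7 = 28). Keep the fatal-TEAE count as a sub-row.
- **Listing:** name in the SAP the protocol's listing of patients who died, with date, cause, days from last dose and source of information. If it is to be dropped, say so in Section 9 with the reason.
- **SAP 8.2.1:** reconcile the carry-over sentence with the worsening clause so that a carried-over AE that becomes fatal is counted, and state where the TEAE window ends.
- **Protocol 8.3.1.8 and 8.3.1.9:** these need to be reconciled on late unrelated SAEs. Until they are, a footnote to the death count should say which reporting rule was applied.

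The cost is one row block and one short listing, from data that the protocol already provides for. The downside is that off-drug deaths enter the table and need the 28-day split to be read correctly.

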8.2. Adverse Events

8.2.1. Summaries of Adverse Event Incidence Rates for All Subjects

Adverse events (AEs) will be coded by System Organ Class (SOC) and Preferred Term (PT) using the Medical Dictionary for Regulatory Activities (MedDRA) version 26.0.

Analyses of AEs will be performed for those events that are considered treatment emergent AEs (TEAEs), where treatment emergence is defined as any adverse events with an onset after initiation of study drug dosing in CY 5032, or an AE present at initiation of study drug dosing that worsens in severity after initiation of study drug dosing. If an AE had the onset in the preceding study CY 5031 and carry over to the open-label extension, it will not be considered as treatment emergent in CY 5032 data.

The following summaries of AEs and serious AEs (SAEs) will be presented by overall:

- TEAEs by SOC and PT
- TEAEs by PT
- TEAEs by SOC, PT and Severity (Grade 1-5)
- TEAEs related to study drug by SOC and PT

- TEAEs related to study drug by PT
- TESAEs by SOC and PT
- TESAEs by PT
- TESAEs related to study drug by PT
- TEAEs leading to drug discontinuation by PT
- TEAEs leading to death

AE summaries will be presented by descending order of PT in the overall column, and if applicable, SOC will be ordered first, with PT sorted within the SOC.

A patient will be counted only once within each SOC and PT. For the summary of AEs by severity, patients will be counted only once within each primary SOC/preferred term and will only be counted under the maximum severity.

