9.2.2. Primary Endpoint

The primary safety endpoint is the incidence of adverse events (AEs) in the patient population.

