1. INTRODUCTION

This document describes the plan for the summarization and analysis of clinical data collected in CY 5032, an open-label extension of CY 5031. CY 5031 was terminated early by the Sponsor due to meeting the futility criteria at the CY 5031 second planned interim analysis. As a result, the analysis scope has been abbreviated, and certain analyses outlined in the protocol will not be conducted, see Section 9 for details.

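### SAP 8.2.1 gives two conflicting rules for an AE that began in CY 5031 and worsens in the extension, and SAP section 9 does not declare the exclusion

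*SAP*

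**What the plan says.** The primary endpoint, in protocol 9.2.2 and again in SAP 2.2.1, is AE incidence: "The primary safety endpoint is the incidence of adverse events (AEs) in the patient population". SAP 8.2.1 restricts the AE analyses to TEAEs and defines a TEAE by two limbs. The first is onset after the first CY 5032 dose. The second is "or an AE present at initiation of study drug dosing that worsens in severity after initiation of study drug dosing". Protocol 9.2.4.1 has the same two limbs and nothing more.

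SAP 8.2.1 then adds a sentence that the protocol does not contain: "If an AE had the onset in the preceding study CY 5031 and carry over to the open-label extension, it will not be considered" treatment emergent in the CY 5032 data.

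On changes from the protocol, the SAP introduction says that "certain analyses outlined in the protocol will not be conducted, see Section 9 for details". Section 9 states that no formal analysis will be produced, that a by-subject listing will be made for liver abnormalities, and that "Only disposition, demographic and baseline characteristics, an overview of AEs and abnormal liver lab results will be summarized by table". It does not mention the TEAE definition.

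**The concern.** The two sentences stand next to each other and classify the same event differently. If the second governs, a carried-over AE that worsens on continued reldesemtiv drops out of the AE summaries. That sits badly with a primary objective of long-term safety and tolerability. Under protocol 2.3.1, every patient entering the extension has already had at least 24 weeks of reldesemtiv, so worsening of an existing event under continued exposure is part of what the study is meant to describe.

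Take an AE that began in CY 5031 and progresses to Grade 5 (fatal, protocol 8.3.1.4) during the extension, still recorded under its CY 5031 onset. The worsening limb makes it a TEAE leading to death. The exclusion removes it from that row.

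**Working it through.** The plan attaches no figure to this point, so the check applies each rule to every possible AE history and then counts the outputs that depend on the answer.

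**Classification by history**

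| AE history | Two-limb definition (SAP 8.2.1, protocol 9.2.4.1) | Carry-over sentence (SAP 8.2.1 only) | Conflict |
|---|---|---|---|
| Onset after first CY 5032 dose | TEAE | silent | no |
| Onset in CY 5031, ongoing, does not worsen | not TEAE | not TEAE | no |
| Onset in CY 5031, ongoing, worsens after first CY 5032 dose | TEAE | not TEAE | **yes** |
| Onset between the end of CY 5031 and first CY 5032 dose, then worsens | TEAE | silent | no |

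The conflict is confined to the third row. SAP 5.7.2 does not settle it, because that section covers only same-day and incomplete dates.

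**What each reading leaves behind**

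- If the carry-over sentence is meant only for events that do not worsen, it adds nothing: the second row shows that those events already fail both limbs.
- If it is applied as written, the worsening limb keeps only the fourth row. SAP 3.1.2 allows the first CY 5032 dose on the day of the CY 5031 Week 48 visit, and for those patients the fourth row is practically empty.

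Either way one of the two sentences has almost no work to do, so two programmers could reasonably set the flag differently.

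**Outputs that depend on the flag**

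- SAP 8.1 overview: any TEAE; serious; drug-related; by severity; leading to dose reduction; leading to treatment discontinuation; leading to death. That is 7 items, and 7 of 7 use the flag.
- SAP 8.2.1 tables on TEAEs: by SOC and PT; by PT; by SOC, PT and severity; related by SOC and PT; related by PT; leading to drug discontinuation; leading to death. That is 7.
- SAP 8.2.1 tables on serious TEAEs: by SOC and PT; by PT; related by PT. That is 3.
- Total: 7 + 3 = 10 tables, and 10 of 10 use the flag. Section 9 keeps only an overview of AEs, so these ten may not all be produced. The 8.1 overview appears to survive.

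**Direction**

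The events counted under the exclusion are a subset of those counted under the two-limb definition. Any count of patients with at least one qualifying event can therefore only stay the same or fall. In the severity rows a patient can drop out or move to a lower maximum grade. A patient's status changes only if the excluded event was that patient's sole qualifying event for the row or, for severity, the highest-grade one.

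**Scale**

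With *n* dosed patients, each patient whose status changes moves a row by 100/*n* percentage points. At the anticipated enrolment of about 400 (SAP 3.2) that is 100/400 = 0.25 points per patient. The study stopped early, so *n* may be smaller and the weight per patient larger. The documents give no number of affected patients.

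**The case against.** The best defence is that the second sentence is a clarification: mere continuation from CY 5031 is not emergence, and the worsening limb just stated still applies. A reading that keeps the limb alive is preferable to one that nearly empties it. This may well be what was intended, but the sentence carries no such qualifier, and on this reading it is redundant. A programmer therefore has reason to give it effect.

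A second argument is that section 9 has nothing to declare if the sentence only clarifies, and that the introduction points to section 9 for analyses not conducted rather than for every departure. The reference in the introduction is indeed that narrow. But section 9 is headed as covering changes to protocol-specified analyses, and an exclusion that overrides the protocol definition of a TEAE is such a change.

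A third argument is that the number of affected events could be nil. Protocol 8.3.1.7 has AEs recorded from the start of study drug. Protocol 8.3.1.1 treats exacerbation of a condition that predates reldesemtiv exposure as an AE in its own right, which can include some CY 5031-onset conditions in patients first exposed in the last 24 weeks of that study. An exacerbation logged with an extension onset counts under either sentence. Against this, protocol 8.3.1.4 keeps a worsening event on one AE page at its worst grade, which suggests that some stay under the old onset. Recording practice is unresolved, so the size is unknown; this does not show it to be zero.

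Finally, other outputs do not use the flag. Disposition (SAP 6.1) reports reasons for discontinuation, and protocol 7.2 lists AE and death among them. AESIs are reviewed individually (SAP 8.2.2), and liver abnormalities are tabulated and listed from laboratory values (SAP 8.5 and 9). Protocol 9.2.4.2 also calls for all SAEs to be summarised and says "Listings will be presented for patients who died and/or experienced serious AEs". These limit the damage. None of them puts an excluded event back into the AE overview. Section 9 does not name the SAE and death listings, and SAP 5.3 promises only unspecified supporting listings, so their survival under the abbreviated scope is unclear.

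**Conclusion.** The concern holds. As written, SAP 8.2.1 gives two answers for one class of event: onset in CY 5031, ongoing at the first CY 5032 dose, worse afterwards. The exclusion, if followed, departs from protocol 9.2.4.1 without being declared.

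The effect runs towards fewer TEAEs and lower maximum grades, within the main safety output that remains. Its reach is 7 of 7 overview items and 10 of 10 listed tables. Its size cannot be stated, because the documents give neither the rate of carried-over or worsening AEs nor the way CY 5031 events are transferred to the CY 5032 CRF. The conclusion assumes only that at least some worsened events stay under their CY 5031 onset. Safety is summarised in one overall group without testing, so no between-group inference is affected. This should be fixed, but it does not threaten the study.

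**What to change.** Replace the carry-over sentence in SAP 8.2.1 with wording such as:

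> An AE that began in CY 5031 and is still present at the first CY 5032 dose is not a CY 5032 TEAE unless its severity increases after that dose. The reference is the last grade recorded before that dose.

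This restores the protocol definition. If full exclusion is what the sponsor wants, restrict the worsening limb to AEs with onset outside CY 5031 and declare the departure from protocol 9.2.4.1 in SAP section 9. A listing of carried-over AEs would help but is optional.

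The cost is a small change to one paragraph, and TEAE counts may be slightly higher. The derivation needs the grade before the first CY 5032 dose, which may have to come from CY 5031 data. Protocol 8.3.1.4 keeps only the worst grade on the AE page; if CY 5031 did the same, some worsening may still go undetected, and the report should say so.
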